14.2 Interim Analysis

The confirmation respective recalculation of sample size for the first primary variables after inclusion of 40 patients will only be performed by estimating the pooled variance (without unblinding). (Refer to section 14.5)

14.3 Level of significance and power

All tests will be conducted with an error of 1st kind $\alpha = 5\%$, two-sided.

Tests of secondary variables will be carried out in the area of exploratory data analysis. Therefore, corresponding p-values are to be regarded as exploratory ones and no adjustments for multiple testing will be made.

Sample size calculations are to be performed with a power of 80%.

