
Duration of Study per Patient
	
Start of study: randomization
 
Treatment period (infusion of Investigational Products):
 
immediately before induction of anesthesia until 12 hours after end of surgery
 
End of study: 12 hours after end of surgery or discharge from ICU / IMC. In case that the discharge is the latest, only its date is to be documented.

Study Schedule
	
Planned start: Q III 2011
 
Planned recruitment time: total sample size 1 year
 
Planned last patient out: Q III / Q IV 2012

Statistical Methods
	
The primary endpoints (BE and chloride) will be tested for difference between the two Gelofusine[®]-groups using a non-parametric statistical test (Mann-Whitney U-Test). This test is chosen with regard to small sample size and possible deviation from normal distribution.
 
All other parameters will be analysed exploratively. This analysis will also serve for testing of homogeneity of treatment groups at baseline.
 
All tests will be performed two-sided with an alpha-error $\alpha = 5\%$.

Randomization / Blinding
	
The patients will be randomised to either treatment in a 1:1 ratio.

	
Randomisation will be performed in permuted blocks.
 
Because of the bicentre study design the population will be stratified with regard to
 
▪ centre
Drug Safety Monitoring Board (DSMB)	not applicable (NA)

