4.2 Study Rationale

In abdominal surgery intra- and postoperative volume replacement is required. Haisch et al. 2001 showed that gelatine solutions are as effective as HES solutions used in abdominal surgery patients.

It is known that infusion of large amounts of colloids in an unbalanced solution like 0.9% NaCl, leads to more-or-less discrete disturbances in acid-base balance (Wilkes, 2001). Base et al. 2011 showed that balanced HES led to a statistically significant reduction in changes of acid base balance and plasma chloride levels when compared with a non-balanced HES. Yunos et al. 2011 showed in their study that the restriction of chloride-rich fluids significantly affected electrolyte and acid-base status in intensive care e.g. the incidence of severe metabolic acidosis (standard base excess (BE) < -5 mEq/L) and decreased significantly. The BE 'removes' the respiratory element of acid-base disturbance and a metabolic acidosis can be diagnosed (Morris CG et al., 2008). Thus BE was chosen as one primary variable. Additionally chloride as another piece of the acid base status was chosen as primary variable. In summary, BE and chloride were chosen as primary variables.

Due to the fact that gelatine polysuccinate as the active substance is well-known and the electrolyte components are physiologically present in the plasma at concentrations not varying significantly from the concentrations in Gelofusine® Balanced the risk due to methods and measurements in the present study the infusion of the new gelatine solution is considered to be low.

Thus, the new gelatine solution, Gelofusine® Balanced, may be a further step into the direction of an ideal volume replacement strategy.

The aim of this prospective, randomized, controlled, double-blind, bicenter study is to demonstrate that acid-base alterations during elective abdominal surgery can be reduced by the use of a balanced gelatine solution compared to a standard gelatine solution.

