14.4 Statistical hypotheses

The primary objective is the verification of a different change in acid base status (ABS) using a balanced gelatine solution combined with a balanced electrolyte solution versus a non-balanced gelatine solution combined with a non-balanced electrolyte solution, so that the following hypotheses need to be tested:

H_0 (null hypothesis):
ABS [balanced] = ABS [non-balanced]

H_A (alternative hypothesis, two-sided):
ABS [balanced] \neq ABS [non-balanced]

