14.5 Sample Size

The primary variables, i.e. base excess (BE) and chloride, are used to calculate the sample size. The data of a study investigating a balanced HES (Wilkes, 2001) served as the basis for the sample size calculation. Due to the fact that it was a comparison of two HES-solutions the results are only an orientation. Therefore these data were adapted. Due to the fact that in this study the reference gelatine solution is already slightly balanced the mean effect regarding chloride were reduced.

Sample size calculation using nQuery Advisor 7.0 resulted in a sample size of 56 patients in total. It was based on the following assumptions:

11 patients per group for chloride, supposing an

- effect size (difference of means/common standard deviation) = 1,711 with difference in means = 6.500.0 and common standard deviation = 3.800,
- error of 1st kind $\alpha = 2.5\%$ (two-sided),
- power = 80% and
- the nonparametric Wilcoxon (Mann-Whitney) test.

28 patients per group for BE, supposing an

- effect size (difference of means/common standard deviation) = -0.910 with difference in means = -3.5 and common standard deviation = 3.847,
- error of 1st kind $\alpha = 2.5\%$ (two-sided),
- power = 80% and

the nonparametric Wilcoxon (Mann-Whitney) test.

In order to account for both parameters and taking a drop out rate of 10% into account, a sample size of 32 patients per group (i.e. 64 patients in total) will be needed.

However, at present no reliable information is available on the acid base status with the new gelatine solution. Thus, an internal pilot phase including 40 patients (including drop-outs) will be performed in order to re-calculate total sample size. For re-calculation the pooled variance will be assessed on the grounds of clinical relevant difference without unblinding. Type I error for both phases of the study will strictly be maintained. (Kieser and Friede, 2000 and 2003).

After sample size adjustment the responsible ethic committees will be asked for approval of study continuation or for termination (e.g. due to futility).

Withdrawn patients will not be replaced because they are considered in the drop out rate.

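### The two primary variables are sized at two-sided 2.5% each but tested at 5% each, and the protocol does not say whether one or both must be significant

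*Protocol*

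**What the plan says.** **Two primary variables.** Section 4.2: "In summary, BE and chloride were chosen as primary variables". The synopsis confirms that both are tested: "The primary endpoints (BE and chloride) will be tested for difference between the two Gelofusine" groups.

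**Level for testing.** Section 14.3: "All tests will be conducted with an error of 1st kind $\alpha = 5\%$, two-sided". The synopsis, directly after naming the two primary endpoints: "All tests will be performed two-sided with an alpha-error $\alpha = 5" percent. Neither place makes an exception for the primary variables.

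**Level for sizing.** Section 14.5 lists "error of 1st kind $\alpha = 2.5\%$ (two-sided") twice, once under chloride and once under BE.

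**Hypothesis.** Section 14.4 gives one pair for an undivided quantity: "The primary objective is the verification of a different change in acid base status (ABS"), with null hypothesis "ABS [balanced] = ABS [non-balanced"]. Section 14.1 likewise speaks of a primary endpoint in the singular. No section says how the BE and chloride results combine into one conclusion.

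**Multiplicity.** The statement in section 14.3 that no adjustment is made belongs to the secondary variables: "Tests of secondary variables will be carried out in the area of exploratory data analysis". The promise in section 14.5 to maintain the type I error refers to the two phases around the blinded sample size re-calculation, not to the two variables.

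**The concern.** A level of 2.5% for each of two variables is a split of an overall 5%. It is needed when significance on either variable can carry the claim. Section 14.3 and the synopsis then drop the split and run each test at 5%. The design and the analysis therefore follow different rules, and the one hypothesis that could settle the matter leaves it open.

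The conflict can change the conclusion of the trial. Suppose one variable has a p-value between 0.025 and 0.05 and the other is not significant. Under an either-variable rule this is a positive trial at the level in section 14.3 and a negative one at the level in section 14.5. Under a both-required rule it is negative in any case. A confirmatory phase III claim should not depend on a choice that can still be made when the results are known.

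**Working it through.** **1. Reproduce the stated sample sizes**

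Inputs from section 14.5: Mann-Whitney test, power 80%, BE effect 3.5/3.847 = 0.910 in absolute value, chloride effect 6.5/3.8 = 1.711. Allocation is 1:1 (section 7.5).

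Noether's formula: n per group = (z(1−α/2) + z(power))² / (6(p − 0.5)²), with p = Φ(effect/√2).

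- p for BE = Φ(0.643) = 0.740. p for chloride = Φ(1.210) = 0.887.
- Numerator at 2.5%: (2.241 + 0.842)² = 9.51. Numerator at 5%: (1.960 + 0.842)² = 7.85.

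| Variable | n per group at 2.5% | n per group at 5% | Stated in 14.5 |
|---|---|---|---|
| BE | 27.50, so 28 | 22.71, so 23 | 28 |
| Chloride | 10.59, so 11 | 8.74, so 9 | 11 |

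Dropout: 28/0.9 = 31.1, so 32 per group and 64 in total, as stated. The sizing rests on 2.5%.

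**2. Family-wise error if either variable suffices**

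The error is the chance of at least one false positive when neither variable differs: 1 − P(|Z₁| < c and |Z₂| < c), with c = 1.960 at 5% and 2.241 at 2.5%. For independent tests at 5% it is 1 − 0.95² = 9.75%. For correlated tests it comes from the bivariate normal distribution. The correlation between the BE and chloride changes is not in the protocol, so the values below are assumptions. The sign does not matter because the tests are two-sided.

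| Assumed correlation | Each at 5% | Each at 2.5% |
|---|---|---|
| 0 | 9.75% | 4.94% |
| 0.5 | 9.07% | 4.65% |
| 0.7 | 8.35% | 4.30% |
| 0.8 | 7.81% | 4.02% |
| 0.9 | 7.04% | 3.62% |

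A simulation of paired Mann-Whitney tests at 28 per group (40,000 trials per setting) gave 9.8%, 9.0%, 8.1%, 7.9% and 7.0% for the 5% column.

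**3. Error if both variables must be significant**

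A false claim then requires a false positive on at least one variable that does not differ, together with significance on the other. The probability cannot exceed the 5% of a single test, so 5% per variable is valid without a split.

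**4. Power at 28 evaluable per group**

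Power = Φ(√(6n)(p − 0.5) − z(1−α/2)), and √(6 × 28) = 12.96.

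- BE at 2.5%: Φ(3.11 − 2.24) = 80.8%. BE at 5%: Φ(3.11 − 1.96) = 87.5%.
- Chloride: 99.7% at 2.5% and 99.9% at 5%.
- Both required at 5% each: at least 87.5% + 99.9% − 100% = 87.4%.
- Holm: BE is tested at 5% once chloride has passed 2.5%, so BE power is at least 87.5% − (100% − 99.7%) = 87.2%.

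**The case against.** **5% may be meant as the overall level.** Section 14.3 could be stating the overall error, with section 14.5 showing its Bonferroni split. The error would then be controlled (at most 5%). This is a plausible account of what the sponsor intended, and it makes the defect one of inconsistent wording more than a deliberate choice of an inflated error rate. But section 14.3 and the synopsis attach 5% to the tests themselves, so the text needs correcting on this reading too.

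**Both variables may be meant to be required.** Section 14.5 takes the larger of the two sample sizes so as to cover both variables. An either-variable rule would not need this, since chloride alone reaches 80% power with 11 per group. If both are required, 5% each is valid. On the other hand, a both-required rule gives no reason for the 2.5% split. The text points both ways, with the split favouring the either-variable rule.

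**The SAP may set the decision rule.** It is not among the documents reviewed here and may do so. The absence of a rule in the protocol is therefore not the main complaint. The protocol itself fixes two incompatible levels, and a SAP that used 2.5% would contradict section 14.3.

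**Two stronger readings that the document does not support.** A reader might infer that the trial's false-positive rate simply is 8–10%. That assumes the either-variable rule, which section 14.4 does not state, and a correlation that the protocol does not give. A reader might also infer that the blinded re-calculation at 40 patients inherits the conflict, since BE needs 28 per group at 2.5% and 23 at 5%. But the re-calculation is described in section 14.5, which uses 2.5% throughout, and section 14.2 refers back to it. Nothing directs it to 5%.

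**Conclusion.** The contradiction stands and needs correcting: 5% per test in section 14.3 and the synopsis, 2.5% per primary variable in section 14.5, and no rule in section 14.4 for combining the two. That part rests on the text alone, and the reproduction of 28 and 11 per group shows that the 2.5% was really used.

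The size of the consequence is conditional. If either variable suffices, testing each at 5% gives a family-wise error of at most 9.75%, and about 7–10% for assumed correlations from 0 to 0.9. If both are required, it is at most 5%. Confidence is high for the contradiction and lower for any single error rate, because the success rule is inferred and the correlation is assumed.

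**What to change.** In sections 14.3 and 14.4 and in the synopsis:

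1. Replace the single acid-base hypothesis by one hypothesis pair for the change in BE and one for the change in chloride.
2. State the success rule and the level that goes with it:
   - **To match the existing sizing:** the trial is positive if at least one variable is significant, with overall two-sided 5% control. Use either 2.5% per variable, as in section 14.5, or Holm's procedure (smaller p-value against 2.5%; if significant, the other against 5%).
   - **If the sponsor intends that both must be significant:** state this, test each at two-sided 5%, and align the level in section 14.5.
3. Limit the general 5% statement to the overall level for the primary variables and to the exploratory tests.
4. Confirm in section 14.5 that the blinded re-calculation uses the level stated for the primary tests.

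The cost is wording in the protocol, carried into the SAP. No patients are added: the planned size stays at 28 evaluable and 32 randomised per group, with BE power of 80.8% at 2.5% or 87.5% at 5%. The rule should be fixed before unblinding.

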14.4 Statistical hypotheses

The primary objective is the verification of a different change in acid base status (ABS) using a balanced gelatine solution combined with a balanced electrolyte solution versus a non-balanced gelatine solution combined with a non-balanced electrolyte solution, so that the following hypotheses need to be tested:

H_0 (null hypothesis):
ABS [balanced] = ABS [non-balanced]

H_A (alternative hypothesis, two-sided):
ABS [balanced] \neq ABS [non-balanced]

14.5 Sample Size

The primary variables, i.e. base excess (BE) and chloride, are used to calculate the sample size. The data of a study investigating a balanced HES (Wilkes, 2001) served as the basis for the sample size calculation. Due to the fact that it was a comparison of two HES-solutions the results are only an orientation. Therefore these data were adapted. Due to the fact that in this study the reference gelatine solution is already slightly balanced the mean effect regarding chloride were reduced.

Sample size calculation using nQuery Advisor 7.0 resulted in a sample size of 56 patients in total. It was based on the following assumptions:

11 patients per group for chloride, supposing an

- effect size (difference of means/common standard deviation) = 1,711 with difference in means = 6.500.0 and common standard deviation = 3.800,
- error of 1st kind $\alpha = 2.5\%$ (two-sided),
- power = 80% and
- the nonparametric Wilcoxon (Mann-Whitney) test.

28 patients per group for BE, supposing an

- effect size (difference of means/common standard deviation) = -0.910 with difference in means = -3.5 and common standard deviation = 3.847,
- error of 1st kind $\alpha = 2.5\%$ (two-sided),
- power = 80% and

the nonparametric Wilcoxon (Mann-Whitney) test.

In order to account for both parameters and taking a drop out rate of 10% into account, a sample size of 32 patients per group (i.e. 64 patients in total) will be needed.

However, at present no reliable information is available on the acid base status with the new gelatine solution. Thus, an internal pilot phase including 40 patients (including drop-outs) will be performed in order to re-calculate total sample size. For re-calculation the pooled variance will be assessed on the grounds of clinical relevant difference without unblinding. Type I error for both phases of the study will strictly be maintained. (Kieser and Friede, 2000 and 2003).

After sample size adjustment the responsible ethic committees will be asked for approval of study continuation or for termination (e.g. due to futility).

Withdrawn patients will not be replaced because they are considered in the drop out rate.

14.6 Data handling

All data will be listed. Whenever applicable all tables, figures and listings will identify patients using the patient identification (ID) and time of evaluation. For data collected prior to randomization, patients will appear in the listings with the treatment to which they were subsequently allocated.

The actual population presented in a table/figure/listing will be mentioned in the headings.

Tables and listings will be produced in accordance with the principles outlined by the ICH E3 guideline.

Handling missing data and outliers

Every effort will be made to collect all data points in the study. The amount of missing data will be minimized by appropriate management of the randomized, prospective, trial, proper screening of subjects, and training of participating investigators and other authorized staff (e.g. nurses), monitors and study co-ordinator. Since all patients who are randomized will be included in the primary analysis, in those instances where data are missing, missing values will not be imputed.

Missing data in tables and listings will be handled as missing data by inserting the symbol ‘.’.

Outliers may be identified using stem-leaf plots and frequency distributions, Scatter and box plots may be also generated for outlier identification. For normally distributed data, values more than three standard deviations away from the mean will be considered outliers. Transformation of the data to mitigate the influence of outliers may be considered. If outliers remain, additional analyses excluding these values will be done and discussed in the report.

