7.4.3 Discontinuation Criteria related to the Patient

The patients will be advised in the Informed Consent Forms that they have the right to withdraw from the study at any time without prejudice, and may be withdrawn at the Investigator's / Sponsor's discretion at any time, when this is considered to be in the interest of the patient.

Withdrawal of individual patients from treatment or from the study respectively could be caused by the following reasons but not limited to

Withdrawn by the Investigator due to

- Adverse Event, Serious Adverse Event (including pregnancy)
- Protocol deviation (e.g. dosing regimen, failure to comply with protocol)
- Administration of an excluded medication
- Clinical significant abnormal laboratory value(s)

which leads to inacceptance of further remaining on treatment or in the study as considered by the investigator.

The patient requested withdrawal due to:

- An Adverse Event for which the Investigator did not consider removal from the treatment/study necessary
- Perceived insufficient therapeutic effect
- Perceived sufficient therapeutic effect
- Withdrawal of consent

In case a patient does not reappear to any scheduled visit (i. e. is lost to follow-up) reasonable effort should be made to contact this patient in order to complete

assessments and/or to evaluate reason for non-appearance (possibly implicit withdrawal of consent).

In the event that a patient withdraws consent or is withdrawn from the study, the study termination page in the CRF (including a final examination, if applicable) should be completed indicating that the study was prematurely terminated. The Investigator should record the date of the withdrawal, the person who initiated withdrawal and the reason for withdrawal.

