9 CONCOMITANT THERAPY

Necessary concomitant medication pre-anesthesia – Patient`s standard medication

- Placement of intravenous and other catheters necessary for the infusion of the investigational products and for monitoring purposes
- Performance of hemodynamic examinations and the obtainment of blood samples for laboratory measurements (see 10)
- Medication as clinically required

Necessary concomitant medication during anesthesia and abdominal surgery:

- Noradrenalin as vasoactive treatment
- Medication as clinically required (e.g. inotropic drugs according to the medical opinion)
- Anesthesia will follow a standardized protocol of a balanced anesthesia using Sevoflurane as volatile anesthetic in combination with a peridural anesthesia where the opioid is arbitrary (left to the standard operating procedure of the study centers):
 - Thoracic peridural catheter (starting with 0.75% Naropin, followed by a mixture of Naropin 0.16% and Sufentanil 0.5 µg/mL using an infusion pump)
 - Anesthesia induction: 1 – 2 mg/kg/BW Propofol
1 – 5 µg/kg/BW Fentanyl
0.5 – 0.6 mg/kg/BW Rocuronium
 - Anesthesia maintenance: Sevofluran

Necessary concomitant therapy during anesthesia and abdominal surgery:

- Ventilation which is aimed at a CO₂ between 38 and 42 mmHg

Volume replacement:

- Administration of investigational products according to the **targets** and **triggers** (see 8.2)
- Administration of blood products according to the following triggers:

Trigger for administration of red blood cells (RBCs) are:

- Hemoglobin (Hb) ≤ 6 g/dL
- Hemoglobin 6 – 8 g/dL, in case of restricted compensation (e.g. coronary heart diseases, cardiac insufficiency and cerebrovascular insufficiency) and / or anemic hypoxia (e.g. tahcaycardia, hyopotension, ischemia and lactatacidose)

Trigger for administration of fresh frozen plasma are:

- Bleeding or
- aPTT > 60s or
- fibrinogen < 2g/dL

Trigger for administration of platelets are:

- Bleeding or
- platelet count < 50.000/ μ L

Unauthorized concomitant medication:

- Administration of other colloid or crystalloid volume replacement agents (e.g. other gelatine solutions, albumin, dextran, HES solutions, other crystalloid solutions) aside from investigational products, with exception of concentrated electrolytes for individual corrections
- Administration of sodium bicarbonate

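### The no-imputation rule in section 14.6 makes the primary analysis complete-case, and withdrawal reasons that can depend on base excess or chloride may then pull the comparison towards no difference

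*Protocol*

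**What the plan says.** **Missing data.** Section 14.6 of the protocol gives a reason and a rule in one sentence. The reason is "Since all patients who are randomized will be included in the primary analysis"; the rule is that "in those instances where data are missing, missing values will not be imputed". Section 14.8 names ITT (full analysis set) as the primary analysis.

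**Endpoint and test.** Sections 5.1.2 and 10.1 define the primary variables as the change in BE and chloride from baseline to immediately after surgery. Section 14.1 tests them with a Mann-Whitney test, with site as covariate in a nonparametric analysis of covariance.

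**Withdrawal.** Section 7.4.3 lists reasons that could lead the investigator to withdraw a patient from treatment or from the study. Two of them are "Clinical significant abnormal laboratory value(s)" and "Administration of an excluded medication". They apply where the investigator judges that the patient cannot acceptably continue. Section 9 lists "Administration of sodium bicarbonate" among unauthorized concomitant medication. On the consequence, section 14.5 states: "Withdrawn patients will not be replaced because they are considered in the drop out rate".

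**Sampling.** Section 10.2.1 schedules arterial blood gases every 15 minutes during surgery, and the table in section 12.2 includes one at end of surgery.

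**The concern.** Including all randomized patients is not a reason to leave values missing. A change score needs both values, so a patient without the later one drops out of the rank test, with or without the site covariate. Taken together, the two halves of the sentence describe a complete-case analysis under an ITT label.

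This matters more than usual here because BE and chloride are themselves laboratory values, and bicarbonate acts directly on BE. Section 11.4 names hyperchloremia and metabolic acidosis as overdose effects of sodium chloride 0.9%, the reference crystalloid. If the trial's hypothesis is right, patients withdrawn for these reasons before the end-of-surgery sample would come mostly from the reference arm and would be its most affected patients. The comparison would then shrink and BE power would fall. The 10% drop-out allowance in section 14.5 replaces lost numbers only; it does not correct for selective loss.

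**Working it through.** **1. The plan's own figure.** Inputs from section 14.5: BE difference 3.5 in size, SD 3.847; chloride difference 6.5, SD 3.8; two-sided alpha 2.5% for each variable; power 80%; drop-out 10%.

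Noether's formula for the Wilcoxon-Mann-Whitney test: n per group = (z_0.9875 + z_0.80)² / [6 (p − 0.5)²], with p = Φ(effect size / √2).

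- BE: effect size 3.5/3.847 = 0.910, p = 0.740, n = 27.5, so 28.
- Chloride: effect size 6.5/3.8 = 1.711, p = 0.887, n = 10.6, so 11.
- Drop-out: 28/0.9 = 31.1, so 32 per group.

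All three stated figures are reproduced.

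**2. Loss that depends on the outcome.** The protocol gives no rate for this, so a range of 3% to 10% of all patients is assumed; 10% is the planned drop-out. BE changes are taken as normal with SD 3.847, mean 0 in the test arm and −3.5 in the reference arm, 32 per group. Patients below a cut-off are lost, and the rest are compared by Mann-Whitney at two-sided 2.5%, without the site covariate (10,000 simulated trials per line).

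| Loss overall | Who is lost below the cut-off | Lost in test / reference arm | BE difference seen | BE power |
|---|---|---|---|---|
| none | – | – | 3.50 | 88.7% |
| 10%, random | – | equal | unbiased | 84.4% |
| 3% | all | 0.6% / 5.4% | 3.12 | 84.1% |
| 5% | all | 1.2% / 8.8% | 2.96 | 80.6% |
| 10% | all | 3.1% / 16.8% | 2.61 | 71.7% |
| 3% | half | 0.8% / 5.2% | 3.20 | 84.8% |
| 5% | half | 1.6% / 8.5% | 3.13 | 83.6% |
| 10% | half | 4.1% / 15.9% | 2.98 | 77.0% |

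Of 64 patients, 3%, 5% and 10% are about 2, 3 and 6.

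**3. Check of the 10% line by hand.** The cut-off is −7.18. The mean of a normal variable kept above c is μ + σ φ(z)/[1 − Φ(z)], with z = (c − μ)/σ.

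- Reference: z = (−7.18 + 3.5)/3.847 = −0.957; mean = −3.5 + 3.847 × 0.2524/0.8307 = −2.33.
- Test: z = −7.18/3.847 = −1.866; mean = 3.847 × 0.0699/0.969 = 0.28.
- Difference: 0.28 + 2.33 = 2.61.

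**4. What does not go wrong.**

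- Chloride, with all of the most affected 10% lost: the difference falls from 6.5 to 5.26, but power stays above 99% (5,000 trials).
- Type I error with no true BE difference and the 10% cut-off applied to both arms: 2.3% against the nominal 2.5%.

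**5. Worst rank.** Keeping the lost patients in the BE test at the lowest rank gives power of 88% to 89% in all six outcome-related scenarios.

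**The case against.** A reader might infer that an abnormal value or bicarbonate takes a patient out of the trial, and that the comparison is therefore biased. The documents do not support this. Section 7.4.3 says only that these reasons could lead to withdrawal, leaves the decision to the investigator, and allows withdrawal from treatment alone.

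The route to a missing endpoint is also narrow. The value is due immediately after surgery, in a patient whose arterial blood is already sampled every 15 minutes. Stopping study product, or leaving after surgery, does not lose it. A patient given bicarbonate who stays in the study has a value; how to use it is a separate question from missing data. Section 14.6 also promises full effort to collect the data, and section 7.4.3 provides for a final examination where applicable.

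The simulated losses are assumptions, and those that remove every patient below the cut-off are close to a worst case. At 3% loss, power matches that of the planned random drop-out; at 5% it still meets the 80% target. Any bias runs against finding a difference. The SAP, not shown here, may define the analysis populations and add sensitivity analyses.

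All of this stands, and it limits the point to a conditional one. It does not repair section 14.6, which fixes the rule in the protocol on a reason that does not support it. Nor does any section require the end-of-surgery blood gas once a patient is withdrawn.

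**Conclusion.** The point holds in conditional form. The stated rule gives a complete-case analysis in place of the ITT analysis of section 14.8. Loss before the end-of-surgery sample may depend on the outcome and may bias the BE and chloride comparisons towards no difference.

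The size depends on a loss rate that the protocol does not give, on normal data with the section 14.5 values, and on losses falling on the most acidotic patients. Over an assumed 3% to 10% loss, the observed BE difference lies between about 3.2 and 2.6 instead of 3.5, and BE power between about 85% and 72% instead of 89%. The chloride estimate shrinks, but its test is hardly affected. No false-positive risk is added. This should be fixed because the remedy is cheap and uncollected values cannot be recovered; it does not invalidate the design.

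**What to change.** Leave the clinical reasons for withdrawal in section 7.4.3 as they are, and change three pieces of wording.

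1. In section 7.4.3, state that stopping study product is not the same as leaving the study. Unless consent is withdrawn, the blood gases already scheduled continue to end of surgery and the patient is analysed as randomized.
2. In section 14.6, replace the sentence quoted above with an explicit rule for patients who still lack an end-of-surgery value.
3. Add a worst-rank sensitivity analysis: lowest rank for BE change, highest for chloride change. It should also cover patients given bicarbonate before the end-of-surgery sample.

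Carrying forward the last sample before bicarbonate as the primary value is debatable. An earlier sample reflects less infused fluid and would probably shrink the difference as well.

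The cost is minor wording and a little extra analysis. No new samples are needed, because gases are already drawn every 15 minutes during surgery.
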